4.2.4.2 Adverse events leading to discontinuation of study medication

AEs with an onset during the short-term double-blind treatment period reported with an action taken of discontinuation of study medication will be summarized by SOC, PT, and treatment group for both the primary and sensitivity safety analyses. This summary will include hypoglycemia and DKA events that are reported as SAEs. When summarizing AEs leading to discontinuation, no upper cutoff day windows (i.e. 4 days and 30 days from last dosing date in the short-term double-blind treatment period for AEs and SAEs respectively) are applied. For short-term double-blind period analyses, the only upper cutoff date is the last date of the short-term double-blind treatment period.

In addition, a subject listing of discontinuation due to AEs will be provided, displaying all events that led to discontinuation with an onset date prior to and including the last date of short-term double-blind treatment period, if any.

4.2.4.3 Confirmed adjudicated cardiovascular adverse events

Cardiovascular events will be independently adjudicated by a Clinical Event Committee (CEC) blinded to the treatment of the subjects in accordance with a dedicated Clinical Event Committee Charter/Manual of Operations: Dapagliflozin Program. All adjudicated cardiovascular events will be summarized by treatment group.

4.2.4.4 Adverse events of special interest

Separate summaries will be provided for the following AEs of special interest. To identify each type of AE of special interest in this section, a list of PTs will be selected before database lock and unblinding of the database. Unless otherwise specified, AEs and SAEs of special interest with an onset from Day 1 of the short-term double-blind treatment period up to and including 4 days and 30 days respectively, after the last dose date in the short-term double-

blind treatment period (or up to the start date of the long-term treatment period, whichever comes first) will be considered as occurring during the short-term double-blind treatment period.

Hepatic adverse events

To facilitate monitoring of liver safety in subjects treated with dapagliflozin, a list of PTs will be selected before database lock of the study to form the Standard MedDRA Query (SMQ) for events of hepatic disorders. The number and percentage of subjects with events of hepatic disorders will be summarized by PT and treatment group in the short-term double-blind treatment period.

Genital Infection

The definition of events of genital infection is based on the dapagliflozin predefined list of events.

The number and percentage of subjects with events of genital infections will be summarized by PT and treatment group in the short-term double-blind treatment period. The number and percentage of subjects with events of genital infections will also be summarized by gender and treatment group in the short-term double-blind treatment period.

The number and percentage of subjects with events of genital infection will be summarized for the subgroups defined on the basis of categorized variables including the frequency of events per subject (recurrence; 1, 2, 3 or > 3), antimicrobial treatment (yes, no or unknown), and additional treatment (yes, no or unknown).

The number and percentage of subjects with events of genital infections qualifying as an SAE will be summarized by PT and treatment group in the short-term double-blind treatment period.

The number and percentage of subjects with events of genital infections leading to discontinuation of double-blind study medication will be summarized by PT and treatment group in the short-term double-blind treatment period.

Time to first event of genital infection will be presented by treatment group using a Kaplan-Meier curve using methodology described in Section 4.1.7. A plot will be presented only when there are at least 5 events in one treatment group. An accompanying table of the cumulative proportion of subjects with time to first genital infections event at specific time points during the short-term double-blind treatment period will be produced.

Urinary-tract Infection

The definitions of events of urinary-tract infection and its subset of kidney infections are based on the dapagliflozin predefined list of events.

The number and percentage of subjects with events of urinary-tract infection and with kidney infections will be summarized by PT and treatment group in the short-term double-blind

treatment period. The number and percentage of subjects with urinary-tract infection will also be summarized by gender and treatment group in the short-term double-blind treatment period.

The number and percentage of subjects with events of urinary-tract infection will be summarized for the subgroups defined on the basis of categorized variables including the frequency of events per subject (recurrence; 1, 2, 3 or > 3), antimicrobial treatment (yes, no, or unknown), additional treatment (yes, no, or unknown).

The number and percentage of subjects with events of urinary-tract infection qualifying as an SAE will be summarized by preferred term and treatment group in the short-term double-blind treatment period.

The number and percentage of subjects with events of urinary-tract infection leading to discontinuation of double-blind study medication will be summarized by PT and treatment group in the short-term double-blind treatment period.

Time to first event of urinary-tract infection will be presented by treatment group using a Kaplan-Meier curve using methodology described in Section 4.1.7. A plot will be presented only when there are at least 5 events in one treatment group. An accompanying table of the cumulative proportion of subjects with time to first urinary-tract infection event at specific time points during the short-term double-blind treatment period will be produced.

A listing of subjects who undergo urine culture will be provided.

Diabetic Ketoacidosis

A DKA Adjudication Committee, blinded to the treatment of the subjects, will independently adjudicate all the DKA events reported by the investigators and those identified based on pre-defined algorithm during the study period. A separate Adjudication Manual will define and describe the procedure for the handling, reporting, and classification of these cases.

DKA events with an onset from Day 1 of the lead-in period up to and including 1 day prior to start of short-term double blind treatment period will be considered as occurring during lead-in period, whereas DKA events with an onset from Day 1 of the short-term double-blind treatment period up to and including 4 days after the last dose date in the short-term double-blind treatment period (or up to the start date of the long-term treatment period, whichever comes first) will be considered as occurring during the short-term double-blind treatment period. The proportion of subjects with DKA events will be tabulated by treatment group in the lead-in period and the short-term double-blind treatment period.

SAEs of DKA with an onset during the short-term double-blind treatment period and leading to discontinuation of study medication will be summarized by treatment group. When summarizing DKA events leading to discontinuation, no upper cutoff day windows are applied.

The number and percentage of subjects with DKA events will be summarized by frequency of events per subject (recurrence; 1, 2, 3, > 3). The total number of events by treatment group will be summarized for the lead in period and the short-term double-blind treatment period.

The exposure adjusted incidence rate of definite DKA events (including recurrences) will be summarized by monthly intervals in order to assess any over time changes in the incidence rate.

Time to first DKA event will be presented by treatment group using a Kaplan-Meier curve using methodology described in Section 4.1.7. A plot will be presented only when there are at least 5 events in one treatment group. An accompanying table of the cumulative proportion of subjects with time to first DKA event at specific time points during the short-term double-blind treatment period will be produced.

A listing of subjects will be produced and it will display all confirmed adjudicated DKA events with an onset date/time from the start date/time of double-blind treatment period up to the start date of the long-term treatment period.

Hypoglycemia

Separate pages to capture events of hypoglycemia are contained within the CRF.

Hypoglycemic events with an onset from Day 1 of the short-term double-blind treatment up to and including 4 days after the last dose date in the short-term double-blind treatment period (or up to the start date of the long-term treatment period, whichever comes first) will be considered as occurring during the Short-term double-blind treatment period.

Hypoglycemic events will be categorized using the following classes following ADA recommendations (Workgroup on Hypoglycemia, American Diabetes Association 2005):

- 1) **Severe hypoglycemia.** “An event requiring assistance of another person to actively administer carbohydrate, glucagons, or other resuscitative actions. These episodes may be associated with sufficient neuroglycopenia to induce seizure or coma. Plasma glucose measurements may not be available during such an event, but neurological recovery attributable to the restoration of plasma glucose to normal is considered sufficient evidence that the event was induced by a low plasma glucose concentration.” (Workgroup on Hypoglycemia, American Diabetes Association 2005)
- 2) **Documented symptomatic hypoglycemia.** “An event during which typical symptoms of hypoglycemia are accompanied by a measured plasma glucose concentration $\leq 70\text{mg/dl}$ (3.9mmol/l).” (Workgroup on Hypoglycemia, American Diabetes Association 2005)
- 3) **Asymptomatic hypoglycemia.** “An event not accompanied by typical symptoms of hypoglycemia but with a measured plasma glucose concentration $\leq 70\text{mg/dl}$ (3.9mmol/l). Since the glycemic threshold for activation of glucagon and epinephrine secretion as glucose levels decline is normally $65\text{--}70\text{mg/dl}$ ($3.6\text{--}3.9\text{mmol/l}$) (24–26) and since antecedent plasma glucose concentrations of $\leq 70\text{mg/dl}$ (3.9mmol/l) reduce sympathoadrenal responses to subsequent hypoglycemia (1,11,20), this criterion sets the lower limit for the variation in plasma glucose in nondiabetic, nonpregnant individuals as

the conservative lower limit for individuals with diabetes.” (Workgroup on Hypoglycemia, American Diabetes Association 2005)

- 4) **Probable symptomatic hypoglycemia.** “An event during which symptoms of hypoglycemia are not accompanied by a plasma glucose determination (but that was presumably caused by a plasma glucose concentration $\leq 70\text{mg/dl}$ [3.9mmol/l]). Since many people with diabetes choose to treat symptoms with oral carbohydrate without a test of plasma glucose, it is important to recognize these events as “probable” hypoglycemia. Such self-reported episodes that are not confirmed by a contemporaneous low plasma glucose determination may not be suitable outcome measures for clinical studies that are aimed at evaluating therapy, but they should be reported.” (Workgroup on Hypoglycemia, American Diabetes Association 2005)
- 5) **Relative hypoglycemia.** “An event during which the person with diabetes reports any of the typical symptoms of hypoglycemia, and interprets those as indicative of hypoglycemia, but with a measured plasma glucose concentration $> 70\text{mg/dl}$ (3.9mmol/l). This category reflects the fact that patients with chronically poor glycemic control can experience symptoms of hypoglycemia at plasma glucose levels $> 70\text{mg/dl}$ (3.9mmol/l) as plasma glucose concentrations decline toward that level (27,28). Though causing distress and interfering with the patient’s sense of well-being, and potentially limiting the achievement of optimal glycemic control, such episodes probably pose no direct harm and therefore may not be a suitable outcome measure for clinical studies that are aimed at evaluating therapy, but they should be reported.” (Workgroup on Hypoglycemia, American Diabetes Association 2005)

The above mentioned classification refers to plasma glucose measurements. In cases where whole blood glucose measurements are reported, they will be converted to plasma equivalent as described in section 6.12.

All analyses of hypoglycemic events will be performed both overall and by class of events as per ADA categorization (Workgroup on Hypoglycemia, American Diabetes Association 2005) presented above.

The proportion of subjects with hypoglycemic events will be tabulated by treatment group in the short-term double-blind treatment period, both regardless of insulin up-titration and, separately, including data only prior to the first post-randomization insulin up-titration by more than 25% relative to baseline.

SAEs of hypoglycemia with an onset during the short-term double-blind treatment period and those leading to discontinuation of study medication will be summarized by treatment group. When summarizing hypoglycemic events leading to discontinuation no upper cutoff day windows are applied. For short-term double-blind period analyses the only upper cutoff date is the start date of the long-term treatment period.

Time to hypoglycemic events leading to discontinuation of study medication will be presented by treatment group using a Kaplan-Meier curve using methodology described in Section 4.1.7. A plot will be presented only when there are at least 5 events in one treatment group. An accompanying table of the cumulative proportion of subjects with time to hypoglycemic

events leading to discontinuation of study medication at specific time points during the short-term double-blind treatment period will be produced.

The number and percentage of subjects with hypoglycemic events will be summarized by frequency of events (recurrence; for severe hypoglycemia: 1, 2, ≥ 3 ; for documented symptomatic hypoglycemia: 1-3, 4-6, or ≥ 7 , for asymptomatic, probable symptomatic, relative hypoglycemia and all hypoglycemic events independently of ADA categorization: 1-5, 6-9, or ≥ 10). The total number of events by treatment group will be summarized for the short-term double-blind treatment period.

The exposure-adjusted incidence rate of hypoglycemic events (including recurrences) will be summarized by monthly intervals in order to assess any over time changes in the incidence rate.

In order to explore any differences in the distribution of hypoglycemic events by randomization strata categories, the proportion of subjects with hypoglycemic events will be summarized for the whole duration of the double-blind treatment period by randomization stratification subgroups. Additionally, this analysis will be repeated by subgroups of change in HbA1c from baseline to Week 24 LOCF (i.e. reduction $\geq 0.5\%$ vs. reduction $< 0.5\%$) and HbA1c week 24 LOCF value (i.e. week 24 LOCF value $< 7\%$ vs. week 24 LOCF value $\geq 7\%$).

A listing of subjects will be produced and it will display all hypoglycemic events with an onset date/time from the start date/time of short-term double-blind treatment period up to the start date of the long-term treatment period.

Hypotension/Dehydration/Hypovolemia

The definitions of hypotension/dehydration/hypovolemia events are based on the dapagliflozin predefined list of events.

The number and percentage of subjects with hypotension/dehydration/hypovolemia events will be summarized by PT and treatment group in the short-term double-blind treatment period.

Renal Impairment/Failure

The definitions of renal impairment/failure events are based on the dapagliflozin predefined list of events.

The number and percentage of subjects with renal impairment/failure events will be summarized by PT and treatment group in the short-term double-blind treatment period.

Fractures

The definitions of events of fracture are based on the dapagliflozin predefined list of events.

The number and percentage of subjects with events of fracture will be summarized by PT and treatment group in the short-term double-blind treatment period.

Hypersensitivity

The definition of hypersensitivity is based on the SMQ of hypersensitivity narrow list.

The number and percentage of subjects with hypersensitivity will be summarized by PT and treatment group in the short-term double-blind treatment period.

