4.2.4.1 Adverse events

Adverse Events (AEs) will be classified by Primary System Organ Class (SOC) and Preferred Term (PT) according to the Medical Dictionary for Regulatory Activities (MedDRA). Summaries of AEs will use the version of MedDRA that is current at the time of database lock.

No statistical test will be performed to compare adverse event rates between treatment groups. This policy was adopted to recognize the lack of power and the potential for misleading

interpretation based on repeated statistical tests which increase the family wise Type I error level.

Counting rules for adverse events are described in Section 6.7.

In summaries by SOC and PT, AEs will be sorted by decreasing frequency within each SOC and PT according to the highest Dapagliflozin dose group. In summaries by PT, AEs will be sorted by decreasing frequency within PT according to the highest dapagliflozin dose group.

Separate pages to capture events of hypoglycemia are contained within the CRF.

Hypoglycemia or discontinuation due to hypoglycemia would not be reported on an AE CRF page unless the event fulfilled criteria for a Serious AE (SAE) in which case an SAE form would be completed. Hypoglycemia events that are reported as SAEs will be included in all summaries of AEs or SAEs (see Section All Adverse Events). Separate summaries will be provided including hypoglycemia events reported on that special CRF pages (see Section Hypoglycemia).

All Adverse Events

All adverse events (serious and non-serious, excluding hypoglycemic and DKA events that are not reported as SAEs) with onset during the short-term double-blind treatment period will be summarized by SOC, PT, and treatment group, for both the primary and sensitivity safety analyses. In addition, a subject listing of all reported adverse events will be produced, displaying all events (including pre-treatment events) that occurred prior to the start date of long-term treatment period. All adverse events (serious and non-serious) including all hypoglycemic events will also be summarized by treatment group.

AEs and SAEs with an onset from Day 1 of the short-term double-blind treatment period up to and including 4 days and 30 days respectively, after the last dose date in the short-term double-blind treatment period (or up to the start date of the long-term treatment period, whichever comes first) will be considered as occurring during the short-term double-blind treatment period.

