In addition, number of subjects reporting any of the following during the double-blind treatment period will be summarized for all treated subjects:

- at least one adverse event
- at least one related adverse event
- deaths
- at least one SAE
- at least one related SAE
- SAE leading to discontinuation of study medication
- AE leading to discontinuation of study medication
- At least one SAE of hypoglycemia
- Hypoglycemia SAE leading to discontinuation of study medication

- At least one SAE of DKA
- DKA SAE leading to discontinuation of study medication

This summary will be repeated for Japanese subjects.

In addition, the following summaries will be provided for the short-term double-blind treatment period (excluding hypoglycemic events that are not reported as SAEs):

- Proportion of subjects with adverse events by SOC and PT in subgroups of subjects defined by age category (<35 years, ≥35 and <50 years, and ≥50 years), gender, and race.
- Most common adverse events by PT and treatment group (i.e., reported by ≥ 5% of subjects in any treatment group),
- Adverse events by SOC, PT, intensity and treatment group,
- Adverse events related to study medication by SOC, PT, and treatment group.

In addition to analyses of event incidence at the subject level, recurrence analyses will be performed at the event level. In order to prepare these summaries, the CRF data will be processed according to standard sponsor algorithms to categorize each line of patient data as a new occurrence or a continuation of an existing event. This determination will be based upon onset and resolution dates. Each line of patient data will represent the maximum severity observed as well as the last known assessed relationship to study medication by the investigator.

The following summary information will be provided:

- Total number and rate (exposure adjusted) of occurrences for all AEs occurring in at least 5% of the subjects treated. This data will be presented as the rate per 100 years of patient exposure. Exposure to study medication will be calculated according to approved standard sponsor algorithms as well. As an example, if 5 patients report 7 unique episodes of headache and had a combined cumulative exposure of 20 years to study medication, the incidence rate is reported as $7 / 20 * (100)$ or 35 cases per 100 patient years of exposure.

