Additionally, a table will be provided displaying the unique instances of all AEs, i.e., after duplicates have been eliminated and overlapping and contiguous occurrences of the same event have been collapsed. No formal comparisons are made between treatments. No formal statistical testing will be performed, only summary statistics are provided.

For the purpose of clinical trial transparency, listing of most common non-serious AEs will be produced for posting at public websites (e.g., NIH's www.ClinialTrials.gov).

Deaths

All deaths recorded on the status page, the AE page, or SAE page (with a death date, cause of death, outcome or SAE categorization present) of the CRF will be considered a death in the analyses. Any deaths that occur during the study will be described in depth as narrative in the

CSR. A listing of all deaths that occur prior to the start date of long-term treatment period will be produced.

Serious Adverse Events

All SAEs (including hypoglycemic events) will be described in narratives, regardless of investigator assessment of causality. SAEs with an onset from Day 1 of the short-term double-blind treatment period up to and including 30 days after the last dose date in the short-term double-blind treatment period (or up to the start date of the long-term treatment period, whichever comes first) will be considered as occurring during the short-term double-blind treatment period.

SAEs occurring during the short-term double-blind treatment period will be summarized by SOC, PT, and treatment group for both the primary and sensitivity safety analyses. In addition, the proportion of subjects with related SAEs will be presented by SOC, PT, and treatment group. A listing of all SAEs will be produced, displaying all SAEs (including pre-treatment events) that occurred prior to the start date of long-term treatment period.

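### For subjects who do not enter the long-term period, serious DKA on days 5-30 after the last dose is in the SAE tables but not the DKA tables, and DKA-specific discontinuation counts cover only SAEs

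*SAP*

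**What the plan says.** **Windows.** The DKA text in SAP 4.2.4.4 places an event in the short-term period if its onset is between Day 1 and "up to and including 4 days after the last dose date in the short-term double-blind treatment period", or before long-term treatment starts if that is sooner. It makes no distinction by seriousness. The proportion and total-event tables use this period. The DKA listing runs to the start of long-term treatment with no day limit. SAP 4.2.4.1 counts SAEs "up to and including 30 days after the last dose date in the short-term double-blind treatment period", with the same cap, and its overview table has the row "At least one SAE of DKA". The general rule at the head of 4.2.4.4 gives AEs of special interest 4 days and SAEs of special interest 30 days; it begins "Unless otherwise specified, AEs and SAEs of special interest with an onset from Day 1".

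**Discontinuation.** The overview has a row "DKA SAE leading to discontinuation of study medication". On the table of AEs leading to discontinuation, SAP 4.2.4.2 says: "This summary will include hypoglycemia and DKA events that are reported as SAEs". The DKA text says: "SAEs of DKA with an onset during the short-term double-blind treatment period and leading to discontinuation of study medication will be summarized". Its next sentence says that no upper day limit applies to DKA leading to discontinuation.

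**All-AE table.** The main table by SOC and PT is drawn up "excluding hypoglycemic and DKA events that are not reported as SAEs".

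**The concern.** DKA is named in the safety objective (SAP 1.1) and has its own blinded adjudication committee. A reader of the report will set the SAE row for DKA beside the DKA tables and the DKA listing. As written, these can give different totals because their windows differ, and the SAP gives no reason for the difference.

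The discontinuation counts have a separate gap. A DKA that was not reported as an SAE but led to stopping study medication has no stated place in any summary that names DKA. Genital and urinary-tract infections are treated differently in the same section: their discontinuation summaries are not limited to SAEs. With few DKA events expected, one event placed differently is noticeable, and it would have to be explained after unblinding.

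**Working it through.** The plan gives no figure to reproduce here, so the check compares the rules and then estimates the scale.

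**1. A serious DKA with onset on day 15 after the last dose, subject not in the long-term period**

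| Output | SAP section | Limit | Counted? |
|---|---|---|---|
| SAE tables and overview row for SAEs of DKA | 4.2.4.1 | 30 days | yes |
| DKA listing | 4.2.4.4 | start of long-term treatment | yes, if confirmed |
| DKA proportion, total DKA events | 4.2.4.4 | 4 days | no |

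For a subject who continues, the start of long-term treatment ends both windows, so the difference essentially vanishes.

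**2. A non-serious DKA that led to stopping study medication, onset within 4 days**

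| Output | SAP section | Counted? |
|---|---|---|
| DKA proportion, total DKA events | 4.2.4.4 | yes |
| Overview row for DKA SAEs leading to discontinuation | 4.2.4.1 | no |
| DKA-specific discontinuation summary | 4.2.4.4 | no |
| Table of AEs leading to discontinuation | 4.2.4.2 | left out by implication only |
| General overview row for AEs leading to discontinuation | 4.2.4.1 | no exclusion stated |
| Discontinuation listing | 4.2.4.2 | yes |

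**3. Cutoff for DKA leading to discontinuation.** The DKA text requires onset in the short-term period, which it has just defined with the 4-day limit. It then says that no upper day limit applies. Section 4.2.4.2 and the hypoglycemia text of 4.2.4.4 also waive the day limits, but each names the cutoff that remains. The DKA text names none.

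**4. Scale of the window difference.**
- Gap: 30 - 4 = 26 days per subject who stops early.
- Randomized: 768 (SAP 1.3).
- Assumed, because the SAP gives neither: 5-20% stop early and do not continue; 2-20 DKA events per 100 patient-years.
- Expected events = 768 x share x 26/365.25 x rate/100.

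| Share | Rate per 100 patient-years | Calculation | All subjects | Per arm (÷ 3) |
|---|---|---|---|---|
| 5% | 2 | 768 x 0.05 x 26/365.25 x 0.02 | 0.05 | 0.02 |
| 10% | 5 | 768 x 0.10 x 26/365.25 x 0.05 | 0.27 | 0.09 |
| 20% | 20 | 768 x 0.20 x 26/365.25 x 0.20 | 2.19 | 0.73 |

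This assumes that every such subject is observed for all 26 days at a constant rate. A higher rate just after stopping would raise the figures. Counting only the serious events would lower them.

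**The case against.** The strongest reply is that the 4-day window is deliberate. The general rule for events of special interest applies only where nothing else is specified; the DKA text specifies something else, and the hypoglycemia text uses the same 4 days. A window close to treatment for the dedicated tables, beside a 30-day window for SAEs, is a legitimate choice. A longer window with a matching denominator would add off-drug time to the rate. This stands: the difference is unexplained but is not a contradiction, and it is no reason to replace the 4-day window.

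A reader might also infer that non-serious DKA leading to withdrawal is in no discontinuation table at all. The SAP does not say that. Section 4.2.4.2 states what its table includes, and the exclusion is only implied. The general overview row states no exclusion, and the listing shows every event that led to discontinuation. What remains is that no count naming DKA is stated to include these events.

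A third reply is that DKA reporting and classification are left to a separate Adjudication Manual. That limits what can be said about how many DKA events would be non-serious. It does not settle which table counts them.

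**Conclusion.** The point holds in a limited form. Followed as written, the SAP leaves out of the DKA proportion and total-event tables serious DKA that it counts in the SAE tables. It restricts the DKA-specific discontinuation counts to SAEs. It also gives two cutoff statements for those counts that need to be reconciled.

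It would go too far to conclude that the plan reports DKA counts that are low in general. Non-serious DKA inside the 4-day window is in the DKA tables whether or not it led to withdrawal. Late events appear in the SAE tables if serious and in the DKA listing if confirmed.

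The window affects only subjects who do not enter the long-term period. Its likely size is about zero to two events in the whole trial under the assumed ranges. The size of the discontinuation gap cannot be estimated from the SAP. The change is worth making because it is cheap and settles in advance why the tables may differ.

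**What to change.** In SAP 4.2.4.4, Diabetic Ketoacidosis:

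1. Keep the 4-day window for the DKA tables. Add one row counting adjudicated DKA with onset up to 30 days after the last dose, or to the start of long-term treatment if sooner. If a rate is given for that row, end its exposure denominator at the same point; the general exposure rule in 6.7.2 stops at the last day of short-term treatment.
2. Summarize all DKA events for which study medication was discontinued, whether or not they were SAEs, and show the SAE subset. Align the DKA row of the overview in 4.2.4.1 and the sentence in 4.2.4.2 with this.
3. Reconcile the two cutoff sentences by naming the start of long-term treatment as the only upper limit for DKA leading to discontinuation, as the hypoglycemia text of the same section already does.

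The cost is a few sentences of SAP wording, one extra table row and a wider discontinuation summary. No new data are needed for the window row beyond the adjudicated events already planned for the listing. The added row may show slightly more events than the 4-day tables, and its label should state its window.
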